4.3 Primary Safety Estimands

4.3.1 Primary Objective 3 from Section 2.3.1 for Group A (Arm 1)

Estimand Description	Probability of adverse events over 72 weeks after the initiation of 2-dose regimen of HEPLISAV-B, in HBV vaccine-experienced adults living with HIV-1 who failed to achieve a protective level of antibodies against HBsAg.
Treatment	2-dose regimen of HEPLISAV-B
Target Population	HBV vaccine-experienced adults living with HIV-1 on ART who failed to achieve a protective level of antibodies against HBsAg, have suppressed HIV-1 RNA and CD4+ T-cell count ≥100 cells/mm³, and initiate 2-dose regimen of HEPLISAV-B vaccination series.
Variable	Occurrence of adverse event (AE) over 72 weeks after vaccine initiation.
Handling of Intercurrent Events	 Incomplete or delayed vaccine series: Participants with incomplete or delayed vaccine series are included. (Treatment Policy Strategy*) Pregnancy: Participants who become pregnant on study have the option of completing the vaccination series and the study. (Principal Stratum Strategy*) Death: Death is considered the worst graded event. (Composite Variable Strategy*)
Population-Level Summary	Proportion of participants.

4.3.2 Primary Objective 3 from Section 2.3.1 for Group A (Arm 2):

Description	Probability of adverse events over 72 weeks after the initiation of 3-dose regimen of HEPLISAV-B, in HBV vaccine-experienced adults living with HIV-1 who failed to achieve a protective level of antibodies against HBsAg.
Treatment	3-dose regimen of HEPLISAV-B
Target Population	HBV vaccine-experienced adults living with HIV-1 on ART who failed to achieve a protective level of antibodies against HBsAg, have suppressed HIV-1 RNA and CD4+ T-cell count ≥100 cells/mm³, and initiate 3-dose regimen of HEPLISAV-B vaccination series.
Variable	Occurrence AE over 72 weeks after vaccine initiation.

Handling of Intercurrent	Incomplete or delayed vaccine series: Participants with incomplete or delayed vaccine series are included. (Treatment Policy Strategy*)
Events	 Pregnancy: Participants who become pregnant on study have the option of completing the vaccination series and the study. (Principal Stratum Strategy*) Death: Death is considered the worst graded event. (Composite Variable Strategy*)
Population-Level Summary	Proportion of participants.

4.3.3 Primary Objective 3 from Section 2.3.1 for Group A (Arm 3)

Description	Probability of adverse events over 72 weeks after the initiation of 3-dose regimen of ENGERIX-B, in HBV vaccine-experienced adults living with HIV-1 who failed to achieve a protective level of antibodies against HBsAg.
Treatment	3-dose regimen of ENGERIX-B
Target Population	HBV vaccine-experienced adults living with HIV-1 and on ART who failed to achieve a protective level of antibodies against HBsAg, have suppressed HIV-1 RNA and CD4+ T-cell count ≥100 cells/mm³, and initiate 3-dose regimen of ENGERIX-B vaccination series.
Variable	Occurrence of AE over 72 weeks after vaccine initiation
Handling of Intercurrent Events	 Incomplete or delayed vaccine series: Participants with incomplete or delayed vaccine series are included. (Treatment Policy Strategy*) Pregnancy: Participants who become pregnant on study have the option of completing the vaccination series and the study. (Principal Stratum Strategy*) Death: Death is considered the worst graded event. (Composite Variable Strategy*)
Population-Level Summary Statistic	Proportion of participants.

4.3.4 Primary Objective 2 from Section 2.3.1 for Group B

Description	Probability of adverse events over 72 weeks after the initiation of 3-dose regimen of HEPLISAV-B, in adults living with HIV-1 without known history of HBV vaccination.
Treatment	3-dose regimen of HEPLISAV-B
Target Population	Adults living with HIV-1 and ART without known history of HBV vaccination who have suppressed HIV-1 RNA and CD4+ T-cell count ≥100 cells/mm³, and initiate 3-dose HEPLISAV-B vaccination series.
Outcome Measure	Occurrence of AE over 72 weeks after vaccine initiation.

Handling of Intercurrent Events	 Incomplete or delayed vaccine series: Participants with incomplete or delayed vaccine series are included. (Treatment Policy Strategy*) Pregnancy: Participants who become pregnant on study have the option of completing the vaccination series and the study. (Principal Stratum Strategy*) Death: Death is considered the worst graded event. (Composite Variable Strategy*)
Population-Level Summary Statistic	Proportion of participants.

4.4 Primary Safety Estimation

4.4.1 Analysis Sets for 4.3.1 - 4.3.4

All participants who have met the study eligibility criteria according to the latest protocol and received any study vaccination will be included in each analysis.

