2.3.1 Primary Objectives

The comparison of SPR between Arms 1 and 3 will be conducted as non-inferiority. Such comparison between Arms 2 and 3 will be conducted as superiority.

Group A

- To compare the week 12 SPR of a two-dose regimen of HEPLISAV-B (Arm 1) versus the week 28 SPR of a standard three-dose regimen of ENGERIX-B (Arm 3) in hepatitis B virus (HBV) vaccine-experienced participants living with HIV.
- 2. To compare the week 28 SPR of a three-dose regimen of HEPLISAV-B (Arm 2) versus a standard three-dose regimen of ENGERIX-B (Arm 3) in HBV vaccine-experienced participants living with HIV.
- 3. To describe adverse events (AEs) reported in each study arm over the duration of the study.

Group B

- 1. To determine the week 28 SPR of a three-dose regimen of HEPLISAV-B in HBV vaccinenaïve participants living with HIV.
- 2. To describe AEs reported over the duration of the study.

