3.1 Primary Outcome Measures

3.1.1 Group A

- [For Primary Objectives 1 and 2] SPR defined as HBsAb ≥10 mIU/mL at 8 weeks after the two-dose series (at Week 12) in Arm 1 and at 4 weeks after the three-dose series (at Week 28) in Arms 2 and 3
- 2. [For Primary Objective 3] Reported AEs from study vaccination initiation to study discontinuation

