4.2 Primary Efficacy Estimation

4.2.1 Analysis Sets for 4.1.1 - 4.1.3

All participants who have met the study eligibility criteria according to the latest protocol and received any study vaccination will be included in each analysis.

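### The primary safety set requires eligibility as well as vaccination, so a vaccinated participant judged ineligible drops out of the primary AE proportions

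*SAP*

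**What the plan says.** SAP 4.4.1 is the only analysis set given for the primary safety estimands (4.3.1-4.3.4). It admits participants who "have met the study eligibility criteria according to the latest protocol and received any study vaccination". The efficacy set in SAP 4.2.1 opens identically, "All participants who have met the study eligibility criteria according to the latest protocol", and continues with the same vaccination condition; SAP 4.6.1 repeats the sentence for the key secondary estimands.

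The safety objectives in SAP 2.3.1 are unconditional: "To describe adverse events (AEs) reported in each study arm over the duration of the study" for Group A and "To describe AEs reported over the duration of the study" for Group B. The matching outcome, in the same words in SAP 3.1.1 and 3.1.2, is "Reported AEs from study vaccination initiation to study discontinuation".

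The target-population rows in 4.3.1-4.3.4 list being on ART, suppressed HIV-1 RNA, a CD4+ count threshold, HBV vaccine history (in Group A, with failure to reach protective antibody), and starting the series: "and initiate 2-dose regimen of HEPLISAV-B vaccination series" for Arm 1, "and initiate 3-dose regimen of ENGERIX-B vaccination series" for Arm 3, "and initiate 3-dose HEPLISAV-B vaccination series" for Group B. SAP 5.2.1 and 5.2.3 then estimate the proportion of participants with AEs, with two-sided 95% Wilson intervals.

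**The concern.** The two conditions in 4.4.1 are joined by *and*, so vaccination alone does not bring a participant into the primary safety analysis. A safety description is meant to cover the people who were exposed. Those vaccinated in breach of a criterion were exposed too, and they need not resemble the rest: criteria visible in the protocol's Letter of Amendment #1 concern recent cancer (4.4.7) and recent inactivated-virus vaccination (4.4.16), either of which could plausibly bear on AE reporting.

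There is also a risk of inconsistency within one report. The AE and death summaries in SAP Section 6, item 7, name no analysis set. The proportions with Grade 2 or higher AEs after injection (Group A Secondary Objective 7, Group B Secondary Objective 4) fall under neither 4.4.1, which covers 4.3.1-4.3.4, nor 4.6.1, which covers 4.5.1-4.5.5. The same people could therefore be counted in some safety tables and left out of the primary one.

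What is at stake is a descriptive estimate for each arm. No between-arm safety test is planned, so no trial conclusion turns on it.

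**Working it through.** **Text check**

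1. *Who is counted.* 4.4.1 requires eligibility and vaccination. No other set in the supplied SAP overrides it.
2. *Does 4.4.2 repair this?* It counts every AE reported on study, but it is a rule about events. Which people contribute events is settled by 4.4.1.
3. *Does the filter simply reproduce the estimand population?* Only in part. A participant can satisfy every element of the target-population rows and still fail exclusion 4.4.7 or 4.4.16. The analysis set is then narrower than the stated target population.

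**Size**

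The plan gives no figure to reproduce here. From the SAP: n = 187 per Group A arm (2.4.1) and n = 73 in Group B (2.4.2), taken as the largest possible denominators. Assumed, because the documents are silent: 2-5% of vaccinated participants ineligible; AE proportion p = 0.30 in eligible and q = 0.60 in excluded participants.

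*Number left out, k:*
- Group A arm: 187 × 0.02 = 3.7 and 187 × 0.05 = 9.4, so about 4 to 9.
- Group B: 73 × 0.02 = 1.5 (1.46 before rounding) and 73 × 0.05 = 3.7, so about 1 to 4.

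*Understatement = (k/n)(q − p):*
- Group A arm: 4/187 × 0.30 = 0.64 points; 9/187 × 0.30 = 1.44 points.
- Group B: 1/73 × 0.30 = 0.41 points; 4/73 × 0.30 = 1.64 points.

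*Bounds with q anywhere from 0 to 1, at the 5% end, p = 0.30:*
- Group A arm: 9/187 × (−0.30 to 0.70) = −1.44 to +3.37 points.
- Group B: 4/73 × (−0.30 to 0.70) = −1.64 to +3.84 points.

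A negative value means the filtered estimate is too high; a positive value means it is too low.

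*Wilson 95% intervals at the 5% end, p = 0.30, q = 0.60:*

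| | Set as in 4.4.1 | All vaccinated |
|---|---|---|
| Group A arm | n = 178: 30.0% (23.8-37.1%) | n = 187: 31.4% (25.2-38.4%) |
| Group B | n = 69: 30.0% (20.5-41.6%) | n = 73: 31.6% (22.1-43.0%) |

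*One rare event, in a participant then judged ineligible:*
- Group A arm: 1/187 = 0.5% (0.1-3.0%) becomes 0/186 = 0% (upper limit 2.0%).
- Group B: 1/73 = 1.4% (0.2-7.4%) becomes 0/72 = 0% (upper limit 5.1%).

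**The case against.** The strongest reply is that the SAP's safety estimands do not target everyone vaccinated. They target a described population, and someone who fails the HIV-1 RNA, CD4+ or vaccine-response condition lies outside it, so leaving that person out is what the estimand asks for. This stands for those criteria. It does not cover people who match the description but fail some other criterion, and it does not explain why the safety objectives and outcomes carry no such restriction.

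Second, the information need not be lost. Items 7a-7c summarise reportable AEs and deaths with no stated eligibility filter, a CONSORT diagram is planned, and SAP 5.1 requires summaries to give the number of participants included. A gap would probably be visible. That is fair, but these items do not correct the primary proportion, and because they name no set the reader cannot be sure whom they count.

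Third, every magnitude above is assumed and the shifts are small against intervals about 13 points wide (Group A arm) and 21 points wide (Group B). This is accepted in full.

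Fourth, the reference to the latest protocol version could be thought to reclassify earlier enrollees. On the visible amendment the changes mostly loosen eligibility, so little weight rests on this.

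Finally, the main protocol body and the Analysis Implementation Plan were not available and might define a safety population. SAP 1.1, however, gives that plan the role of outlining tables, figures and coding, while the SAP itself sets out the analysis sets in Section 4.

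**Conclusion.** The concern holds. As written, the primary AE proportions for Group A Primary Objective 3 and Group B Primary Objective 2 leave out any vaccinated participant judged ineligible. The number of such participants is unknown and may be zero. Under the stated assumptions the effect on a common AE is at most a few percentage points in either direction and well inside the confidence interval. It matters more for rare events, where one exclusion can turn a non-zero estimate into zero. The point is worth fixing because it removes a possible selection bias from a primary safety estimate at almost no cost. The unstated set for item 7 and the post-injection summaries is a lesser documentation gap. Confidence is medium, given the documents not seen.

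**What to change.** - Change SAP 4.4.1 to: *All participants who received any study vaccination.*
- Align the target-population rows in 4.3.1-4.3.4 with that set.
- State that report item 7 and the Grade 2 or higher post-injection AE summaries (Group A Secondary Objective 7, Group B Secondary Objective 4) use the same set. In the same sentence, say whether participants are tabulated by assigned or received vaccine.
- Optional, and separate from safety: an all-vaccinated sensitivity analysis of the primary SPR comparisons by assigned arm.

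Without the optional analysis, the cost is one revised sentence in 4.4.1, four table rows, and one added sentence. No new data are needed.

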4.4.2 Details on Outcome Measures for 4.3.1 – 4.3.4

All adverse events reported during the study will be included.

4.4.3 Handling of Missing Data for 4.3.1 - 4.3.4

For participants who discontinue study prior to Week 72, assume no additional adverse events occur after loss to follow-up. A sensitivity analysis may be conducted where censoring occurs at the last study visit to estimate proportion using a time-to-event method.

4.5 Key Secondary Estimands

4.5.1 Secondary Objective 1 from Section 2.3.2 for Group A

Description	Difference in the mean antibody titers between 2-dose regimen of HEPLISAV-B and 3-dose regimen of ENGERIX-B in HBV vaccine-experienced adults living with HIV-1 who failed to achieve a protective level of antibodies against HBsAg.
Treatment	2-dose regimen of HEPLISAV-B vs. 3-dose regimen of ENGERIX-B
Target Population	HBV vaccine-experienced adults living with HIV-1 on ART who failed to achieve a protective level of antibodies against HBsAg, have suppressed HIV-1 RNA and CD4+ T-cell count ≥100 cells/mm³, and initiate vaccination series.
Variable	HBsAb titer at 12 weeks after the initiation of the HEPLISAV-B vaccine series, or HBsAb titer at 28 weeks after the initiation of the ENGERIX-B vaccine series.
Handling of Intercurrent Events	 Incomplete or delayed vaccine series: Participants with incomplete or delayed vaccine series are included. (Treatment Policy Strategy*) Pregnancy: Participants who become pregnant on study have the option of completing the vaccination series and the study. (Principal Stratum

	Strategy*) 3. Death: Participants who die prior to completion of vaccine series are included. (Treatment Policy Strategy*)
Population-Level Summary	Difference in the geometric mean titer (GMT).

4.5.2 Secondary Objective 2 from Section 2.3.2 for Group A

Description	Difference in the mean antibody titers between 3-dose regimen of HEPLISAV-B and 3-dose regimen of ENGERIX-B in HBV vaccine-experienced adults living with HIV-1 who failed to achieve a protective level of antibodies against HBsAg.
Treatment	3-dose regimen of HEPLISAV-B vs. 3-dose regimen of ENGERIX-B
Target Population	HBV vaccine-experienced adults living with HIV-1 and on ART who failed to achieve a protective level of antibodies against HBsAg, have suppressed HIV-1 RNA and CD4+ T-cell count ≥100 cells/mm³, and initiate vaccination series.
Variable	HBsAb titer at 28 weeks after the initiation of the vaccine series.
Handling of Intercurrent Events	 Incomplete or delayed vaccine series: Participants with incomplete or delayed vaccine series are included. (Treatment Policy Strategy*) Pregnancy: Participants who become pregnant on study have the option of completing the vaccination series and the study. (Principal Stratum Strategy*) Death: Participants who die prior to completion of vaccine series are included. (Treatment Policy Strategy*)
Population-Level Summary	Difference in GMT.

4.5.3 Secondary Objective 3 from Section 2.3.2 for Group A on SPR at 48 Weeks After Last Vaccination

Description	Difference in the probabilities of long-term SPR between 2-dose regimen of HEPLISAV-B and 3-dose regimen of ENGERIX-B in HBV vaccine-experienced adults living with HIV-1 who failed to achieve a protective level of antibodies against HBsAg.
Treatment	2-dose regimen of HEPLISAV-B vs. 3-dose regimen of ENGERIX-B
Target Population	HBV vaccine-experienced adults living with HIV-1 and on ART who failed to achieve a protective level of antibodies against HBsAg, have suppressed HIV-1 RNA and CD4+ T-cell count ≥100 cells/mm³, and initiate vaccination series.
Variable	SPR at 52 weeks after initiation of 2-dose vaccine series and at 72 weeks after initiation of 3-dose vaccine series.

Handling of Intercurrent Events	 Incomplete or delayed vaccine series Participants with incomplete or delayed vaccine series are included. (Treatment Policy Strategy*) Pregnancy: Participants who become pregnant on study have the option of completing the vaccination series and the study. (Principal Stratum Strategy*) Death: Participants who die prior to completion of vaccine series are included. (Treatment Policy Strategy*)
Population-Level Summary	Difference in proportions.

4.5.4 Secondary Objective 3 from Section 2.3.2 for Group A on GMT at 48 Weeks After Last Vaccination

Description	Difference in the long-term mean titers between 2-dose regimen of HEPLISAV-B and 3-dose regimen of ENGERIX-B in HBV vaccine-experienced adults living with HIV-1 who failed to achieve a protective level of antibodies against HBsAg.
Treatment	2-dose regimen of HEPLISAV-B vs. 3-dose regimen of ENGERIX-B
Target Population	HBV vaccine-experienced adults living with HIV-1 on ART who failed to achieve a protective level of antibodies against HBsAg, have suppressed HIV-1 RNA and CD4+ T-cell count ≥100 cells/mm³, and initiate vaccination series.
Variable	HBsAb titer at 52 weeks after initiation of 2-dose vaccine series and at 72 weeks after initiation of 3-dose vaccine series.
Handling of Intercurrent Events	 Incomplete or delayed vaccine series: Participants with incomplete or delayed vaccine series are included. (Treatment Policy Strategy*) Pregnancy: Participants who become pregnant on study have the option of completing the vaccination series and the study. (Principal Stratum Strategy*) Death: Participants who die prior to completion of the vaccine series are included. (Treatment Policy Strategy*)
Population-Level Summary	Difference in GMT.

4.5.5 Secondary Objective 1 from Section 2.3.2 for Group B

Description	Mean titer of HBsAb after HEPLISAV-B vaccination in adults living with HIV-1 without known history of HBV vaccination.
Treatment	3-dose regimen of HEPLISAV-B
Target Population	Adults living with HIV-1 and on ART without known history of HBV vaccination who have suppressed HIV-1 RNA and CD4+ T-cell count ≥100 cells/mm³, and initiate vaccination series.
Variable	HBsAb titer at 28 weeks after initiation of the vaccine series.

Handling of	Incomplete or delayed vaccine series: Participants with incomplete or
Intercurrent	delayed vaccine series are included. (Treatment Policy Strategy*)
Events	 Pregnancy: Participants who become pregnant on study have the option of completing the vaccination series and the study. (Principal Stratum Strategy*) Death: Participants who die prior to completion of vaccine series are included. (Treatment Policy Strategy*)
Population-Level	GMT
Summary	

4.6 Key Secondary Estimation

4.6.1 Analysis Sets for 4.5.1 - 4.5.5

All participants who have met the study eligibility criteria according to the latest protocol and received any study vaccination will be included in each analysis.

4.6.2 Details on Outcome Measures for 4.5.1 – 4.5.5

- For HBsAb titer at 12 weeks after the initiation of the 2-dose series and for 28 weeks after
 the initiation of the 3-dose series (Secondary Estimands in Sections 4.5.1, 4.5.2 and
 4.5.5), antibody results corresponding to SPR measurements described in Section 4.2.2
 will be used.
- For HBsAb titer at 52 weeks after the initiation of the 2-dose series and 72 weeks after
 the initiation of the 3-dose series (Secondary Estimands in Sections 4.5.3 and 4.5.4),
 antibody results at Week 52 study visit and at Week 72 study visit, respectively, will be
 used.

4.6.3 Handling of Missing Data for 4.5.1 - 4.5.5

Each analysis on antibody titers will be conducted on participants with available data, under the assumption of missing completely at random (Li, Wang, Liu, Chan, 2011).

A sensitivity analysis will be conducted for the missing HBsAb titer data at 12 weeks after the initiation of the 2-dose series and for 28 weeks after the initiation of the 3-dose series (Secondary Estimands in Sections 4.5.1, 4.5.2 and 4.5.5), with imputations analogous to what was described for SPR in Section 4.2.3 in the case that the total missing SPR results is >10%.

A sensitivity analysis will be conducted for the missing HBsAb titer data at 52 weeks after the initiation of the 2-dose series and 72 weeks after the initiation of the 3-dose series (Secondary Estimands in Sections 4.5.3 and 4.5.4), where the missing value will be imputed with the result from the subsequent visit, if there are >10% such imputations.

5 Analysis Considerations

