#### 10. Table 6.1-1 Group A (Arm 1 only)

Pregnancy testing at screening was removed as shown below:

Evaluations	Screening	Entry (Day 0)		Po		Premature Study				
			4	8	12	24	28	52	72	Discontinuation
Visit Windows	Within 45 days	≥24 hours after screening	-4/+7 days	+ / da				±14	days	Evaluations (*refer to section 6.2.4)
Pregnancy Testing	X	X	X						Χ	X

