# 11. Table 6.1-2 Group A (Arms 2 and 3 only)

Pregnancy testing at screening was removed as shown below:

Evaluations	Screening	Entry (Day 0)	,		3		Pos	st-Er	ntry I (We			ons		
		(Day 0)	Evaluation	4	8	12	24	28	32	48	72	Premature		
Visit Windows	Within 45 days	≥24 hours after screening	≥16 to ≤28 hours post 1 st vaccination; at US sites only and is optional	-4/+7 days		±7	7 da .	ys			14 nys	Study Discontinuation Evaluations (*refer to section 6.2.4)		
Pregnancy Testing	X	Χ		Χ			Χ				Χ	X		

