### **Remote Data Collection**

Study visits may be conducted remotely (e.g., telephone, telehealth) in the following situations:

- A participant is unable to attend a visit because of illness, lockdown status, or quarantine; the site must inform the CMC ([contact])
- The site is temporarily unable to conduct non-essential visits in the clinic; the site must inform the CMC ([contact])

Remote visits should be conducted during the visit window according to the SOE. Regardless of the situation, sites should document which visits were conducted remotely. For visits that are conducted remotely, the site should attempt to obtain as much of the visit-specific required information based on the SOE as possible and record it on the relevant eCRF.

In addition to the remote visit, the participant should be scheduled for an in-person visit for all evaluations that were not conducted at the remote visit. If the in-person visit evaluations are outside of the visits window, have the participant in as soon as possible for safety-related evaluations as an unscheduled visit, but if within a week of the next scheduled visit window, then wait for the next scheduled visit and add any safety lab evaluations not already being performed. If the participant is unable or prefers not to come to the site for a visit, priority safety labs are permitted to be done at a local lab or as part of the standard of care. Record these on an eCRF. The priority safety labs include: chemistry, hematology, and liver function tests.

We ask the sites to prioritize sample collection for HBsAb testing at Week 12 for Arm 1 in Group A, and Week 28 for Arms 2 and 3 in Group A and for Group B. If there is a need to limit in-person interactions at the site, the in-person component can be restricted to the blood draw, and the remaining visit evaluations can be completed remotely.

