3.2 Secondary Outcome Measures

3.2.1 Group A

- 1. HBsAb titer at the following study visits in Arm 1:
 - a. Week 4 [Secondary Objective 6]
 - b. Week 8 [Secondary Objectives 3, 5, and 6]
 - c. Week 12 [Secondary Objectives 1, 3, 5, and 6]
 - d. Week 24 [Secondary Objective 6]
 - e. Week 28 [Secondary Objectives 3 and 5]
 - f. Week 52 [Secondary Objectives 3 and 5]
 - g. Week 72 [Secondary Objective 9]
- 2. SPR defined as HBsAb ≥10 mIU/mL at the following study visits in Arm 1:
 - a. Week 4 [Secondary Objective 6]
 - b. Week 8 [Secondary Objectives 3, 5, and 6]
 - c. Week 12 [Secondary Objectives 3, 5, and 6]
 - d. Week 24 [Secondary Objective 6]
 - e. Week 28 [Secondary Objectives 3 and 5]
 - f. Week 52 [Secondary Objectives 3 and 5]
 - g. Week 72 [Secondary Objective 9]
- 3. HBsAb titer at the following study visits in Arm 2:
 - a. Week 4 [Secondary Objective 6]
 - b. Week 8 [Secondary Objective 6]
 - c. Week 12 [Secondary Objective 6]
 - d. Week 24 [Secondary Objective 6]
 - e. Week 28 [Secondary Objectives 2 and 5]
 - f. Week 32 [Secondary Objectives 4 and 5]
 - g. Week 48 [Secondary Objectives 4 and 5]
 - h. Week 72 [Secondary Objectives 4, 5, and 9]
- 4. SPR defined as HBsAb ≥10 mIU/mL at the following study visits in Arm 2:
 - a. Week 4 [Secondary Objective 6]
 - b. Week 8 [Secondary Objective 6]
 - c. Week 12 [Secondary Objective 6]
 - d. Week 24 [Secondary Objective 6]
 - e. Week 28 [Secondary Objective 5]
 - f. Week 32 [Secondary Objectives 4 and 5]
 - g. Week 48 [Secondary Objectives 4 and 5]
 - h. Week 72 [Secondary Objectives 4, 5, and 9]
- 5. HBsAb titer at the following study visits in Arm 3:
 - a. Week 4 [Secondary Objective 6]
 - b. Week 8 [Secondary Objective 6]

- c. Week 12 [Secondary Objective 6]
- d. Week 24 [Secondary Objective 6]
- e. Week 28 [Secondary Objectives 1, 2 and 3]
- f. Week 32 [Secondary Objectives 3 and 4]
- g. Week 48 [Secondary Objectives 3 and 4]
- h. Week 72 [Secondary Objectives 3 and 4]
- 6. SPR defined as HBsAb ≥10 mIU/mL at the following study visits in Arm 3:
 - a. Week 8 [Secondary Objective 6]
 - b. Week 12 [Secondary Objective 6]
 - c. Week 24 [Secondary Objective 6]
 - d. Week 28 [Secondary Objective 3]
 - e. Week 32 [Secondary Objectives 3 and 4]
 - f. Week 48 [Secondary Objectives 3 and 4]
 - g. Week 72 [Secondary Objectives 3 and 4]
- 7. Grade ≥2 AEs within 4 weeks after each injection [Secondary Objective 7]

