4.2.3 Handling of Missing Data for 4.1.1 - 4.1.3

Each analysis on SPR will be conducted on participants with available data, under the assumption of missing completely at random (Li, Wang, Liu, Chan, 2011).

A sensitivity analysis will be conducted with the following imputations.

- Missing SPR will be imputed if both antibody results immediately prior to and after the
 missed visit are <10 mIU/mL, or if both are ≥10 mIU/mL. This is assuming that there is no
 change in the response between the visits where data are available.
- If after the above imputation, the total missing SPR results is >10% (above what was accounted for in the study design), then the following additional imputation will be made in the sensitivity analysis:
 - For the recipients assigned to 3-dose vaccine series, the antibody result from the subsequent visit that occurs within 4 weeks of the missed SPR visit will be used to allow the result from Week 32 study visit, accounting for the visit window.

For the recipients assigned to 2-dose vaccine series, the antibody result from a visit within 4 weeks of the missed SPR visit (8 weeks after the vaccine series) will be used to allow the result from Week 8 study visit (4 weeks after the vaccine series) or from an unscheduled visit that occurs subsequent to the missed visit within 4 weeks. The visit window from the protocol schedule of evaluations will be applied.

The number of imputations in the sensitivity analysis will be summarized by study arm.

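### The sensitivity analysis for 48-week durability imputes from the next visit, but Arm 3 has no visit after Week 72, so under the schedule only Arm 1 can be imputed

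*SAP*

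**What the plan says.** SAP 4.5.3 (SPR) and 4.5.4 (GMT) compare Arm 1 with Arm 3 at 48 weeks after the last dose. SAP 4.6.2 takes this from the Week 52 visit in Arm 1 and the Week 72 visit in Arm 3. The main analysis uses available data and assumes missing completely at random.

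SAP 4.6.3 then adds one sensitivity analysis for these outcomes, "where the missing value will be imputed with the result from the subsequent visit, if there are >10% such imputations". The paragraph just before it, on the Week 12 and Week 28 titers, has a different trigger: it applies "in the case that the total missing SPR results is >10" per cent.

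In SAP 3.2.1 the final Arm 3 titer entry is "h. Week 72 [Secondary Objectives 3 and 4", and nothing follows it. In Arm 1 the entry after Week 52 is "g. Week 72 [Secondary Objective 9". The visit tables reproduced in the protocol's letter of amendment agree: Week 72 is the last scheduled visit for Arms 2 and 3, and in Arm 1 Week 52 is followed by Week 72. SAP 1.1 places study completion at Week 72.

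**The concern.** A rule that takes the replacement value from the next visit needs a next visit. Arm 3 has none, so half of the rule cannot be carried out on schedule. In Arm 1 it can be, but with a sample taken well past the target time. If titers wane, the comparison then moves against Arm 1 only.

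The SAP's own safeguards for the primary outcome (4.2.3) are not carried over. There the first step starts "Missing SPR will be imputed if both antibody results immediately prior to and after the" missed visit agree. It has no time limit, but it needs concordant results on both sides. The second step substitutes a single visit directly, but only within 4 weeks. The durability rule has neither condition.

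This matters because it is the only planned missing-data check on these two estimands. The supplementary analyses in SAP section 6, item 13 cover Secondary Objectives 1 and 2, not the 48-week comparison. SAP 2.5.1 gives the long-term antibody data as the reason for not concluding non-inferiority early. SAP 1.2 says the missing-data rules were extended because the pandemic might cause more missing data than planned.

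**Working it through.** **Base sample size (SAP 2.4.1).** Inputs: 75% and 70% SPR, margin 10%, one-sided 1.25%, power 80%.

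n = (2.241 + 0.842)² × (0.75×0.25 + 0.70×0.30) / (0.05 + 0.10)² = 9.505 × 0.3975 / 0.0225 = 167.9, so 168. Then 168/0.9 = 186.7, so 187 per arm. Both stated figures reproduce.

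**Replacement visit, by arm.**

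| | Last dose | Target visit | Next scheduled visit | Gap | Weeks after last dose: target / replacement |
|---|---|---|---|---|---|
| Arm 1 | Week 4 | Week 52 | Week 72 | 72 − 52 = 20 weeks | 48 / 68 |
| Arm 3 | Week 24 | Week 72 | none | – | 48 / none |

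The 20 weeks is nominal. With a ±14-day window on Week 72, the replacement falls 18 to 22 weeks after nominal Week 52.

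**Trigger.** The denominator for the 10% is not stated.
- Arm 1 alone: 10% of 187 = 18.7, so 19 imputations (19/187 = 10.2% of Arm 1).
- Arms 1 and 3: 10% of 374 = 37.4, so 38 imputations, all from Arm 1 (38/187 = 20.3%).

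Arm 3 with 10%, 20% or 30% missing (19, 38 or 56 participants) supplies 0 scheduled imputations. Two mixed cases:
- 5% missing in Arm 1 and 30% in Arm 3: (9 + 56)/374 = 17.4% of results are missing. At most 9 can be imputed (4.8% of Arm 1, 2.4% of both arms), so the analysis does not run on either denominator.
- 15% missing in each arm: at most 28 imputations, all in Arm 1. It runs on the Arm 1 denominator (15.0%) but not on the two-arm denominator (7.5%).

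**Size of the shift once triggered.** The documents give no waning rate, titer SD or durability SPR. Assumed: waning 0.2–0.5 log10 per year, log10 SD 0.8–1.2, Arm 1 Week 52 SPR 60–90%, normally distributed log10 titer.
- Each imputed titer is too low by 0.2×20/52 = 0.077 to 0.5×20/52 = 0.192 log10.
- GMT: 0.102×0.077 = 0.008 to 0.203×0.192 = 0.039 log10, a factor of 0.982 to 0.914.
- 95% half-width for GMT, with 187 in Arm 1 after imputation and 168 in Arm 3: 1.967 × SD × √(1/187 + 1/168) = 0.167 (SD 0.8) to 0.251 (SD 1.2). The shift is 0.008/0.251 = 3% to 0.039/0.167 = 23% of it.
- SPR among those imputed falls by p − Φ(z_p − d/SD), where d is the titer deficit: from 1.2 points (p 0.90, SD 1.2, d 0.077) to 9.5 points (p 0.60, SD 0.8, d 0.192). Multiplied by 0.102 and 0.203, Arm 1 falls by 0.12 to 1.93 points.
- 97.5% half-width for SPR, by a simple unstratified approximation: 2.241 × √(p(1−p)(1/187 + 1/168)) = 7.1 points (p 0.90) to 11.7 points (p 0.60). The shift is 1.7% to 16.5% of it.

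Arm 3 does not change in any of these cases.

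**The case against.** **The trigger may mean values that would need imputing.** It can be read loosely that way, in line with the preceding paragraph. On that reading Arm 3 missingness could start the analysis. The literal wording counts imputations, however, and on either reading Arm 3 still has no scheduled value to impute from.

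**A late or unscheduled Arm 3 sample could serve.** This is possible, but 4.6.3 does not mention one, whereas 4.2.3 does for the two-dose series. The letter of amendment asks for an in-person visit to complete what a remote visit left out. Outside the window it says to "have the participant in as soon as possible for safety-related evaluations as an unscheduled visit", so an antibody draw is not assured. That text covers remote visits only and adds little to what the schedule already shows.

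**The upper magnitudes are a corner case.** They need everyone who misses Week 52 to return at Week 72. This is fair. If half of those missing had dropped out (an assumption), 19 imputations would need 38 missing (20% of Arm 1) and 38 would need 76 (41%). Arm 1 dropouts have no replacement value either. This makes the trigger rarer; it does not reduce the shift at a given number of imputations. Participants with little antibody also cannot wane by the full assumed amount.

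**The bias is conservative for Arm 1, and Arm 3 loss would be visible.** Both are true. Discontinuations are listed and numbers with data are reported. Neither tests whether missing Arm 3 values alter the comparison.

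**Conclusion.** The concern holds. Under the schedule, the sole missing-data check on estimands 4.5.3 and 4.5.4 can impute Arm 1 only, from a sample nominally 20 weeks past target, and as worded Arm 3 missingness essentially cannot activate it. These structural points follow from the documents and need no assumption beyond the visit schedule being followed.

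The numerical effect rests on the assumed waning, SD and SPR, and is modest: at most about a quarter of the GMT interval half-width and about a sixth of the SPR half-width. The reason to act is the untested arm. The reach is limited to a conditional sensitivity analysis of key secondary estimands. It should be fixed, and it does not threaten the primary results.

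**What to change.** In SAP 4.6.3:
- Run the sensitivity analysis when more than 10% of durability results are missing in either arm, counting missing results, not imputations.
- Replace the next-visit rule with one that both arms can carry out and that targets Week 52 in Arm 1 and Week 72 in Arm 3. One suitable option is multiple imputation of log10 titer within arm from the post-series visits already collected (Arm 1 Weeks 8, 12, 24, 28, 52 and 72; Arm 3 Weeks 28, 32, 48 and 72), with SPR derived from the imputed titers. The SAP should also say how values near the assay floor are handled.
- Report the number imputed by arm.

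The cost is SAP wording and modest programming, with no new visits or samples. The downside is that multiple imputation assumes missing at random given the observed titers, so by itself it does not probe informative dropout.
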